# 8. Study population

#### Inclusion criteria:

- Patients with medial and lateral compartment osteoarthritis of the knee with intact cruciate ligaments
- Patients over the age of 18 (no upper restriction)
- Patients of any BMI
- Patients willing and able to give informed consent

#### Exclusion criteria:

- Patients with osteoarthritis limited to one compartment of the knee
- Patients with rheumatoid Arthritis
- Patients with medial or lateral subluxation of the tibia on the femur
- Patients with a varus or valgus deformity greater than 15°
- Patients with a flexion contracture greater than 10°
- Patients with rupture of either the ACL or PCL
- Active or recent local infection
- Patello-femoral OA greater than Kellgren and Lawrence grade III
- Patients who have had previous surgery to the knee which may impact on the outcome of TKA or Bi-Unicompartmental Knee Arthroplasty
- Patients who are currently awaiting bi-lateral knee replacement surgery
- · Patients with significant disease in other joints which might impact on their gait
- Patients unable to give informed consent

#### 9. Planned interventions

Patients will be randomised to one of two interventions.

**Group 1- Standard TKA (Control):** Patients receiving TKA will be have a fixed bearing, cruciate sacrificing posterior stabilised Zimmer NexGen LPS TKA. These will be implanted using traditional surgical techniques and without the aid or robotics of navigation. This is the current standard of care treatment at the investigative centre and the routine method of TKA implantation in the majority of centres in the UK currently.

Mechanical axis targets for limb alignment for this group will be zero degrees.

**Group 2- Robotic assisted Bi-UKA (Experimental):** Patients randomising to Bi-UCKA will receive two unicondylar fixed bearing MAKO Restoris MCK implants, one implanted on the medial side of the knee and the other on the lateral side. These implants will be inserted with the aid of robotic assistance using the MAKO RIO Robotic System. A midline incision with medial and lateral quadriceps sparing parapatellar approaches will be used.

There are no fixed mechanical axis targets for the Bi-UCKA group. Instead the surgeon will aim to restore the constitutional angle of the joint.

All other pre and peri-operative factors will be equal for both groups. All patients will receive a spinal anaesthetic combined with peripheral nerve block and prophylactic antibiotics. Above knee tourniquets will be used routinely. Post-operative rehabilitation will consist of daily physiotherapy for the duration of the patients stay in hospital. After discharge a routine physiotherapy class will be offered for 7-14 days after surgery. Additional physiotherapy will only be offered to those patients who fail to achieve standard rehabilitation milestones and in particular those with restricted range of motion. The need for additional physiotherapy will be determined by a blinded practitioner.

# 9.1. Study devices

- MAKO Restoris Multi Compartmental Knee (MCK) System (MAKO Surgical Corp., Fort Lauderdale, Florida, USA). THE MCK system offers a choice of tibial components onlay or inlay. For the purposes of this study only the tibia onlay system will be used. All components are currently CE marked for use in Medial Unicompartmental or Lateral Unicompartmental Knee replacement, but not both medial and lateral combined in a single joint.
- Zimmer NexGen Legacy Posterior Stabilised (LPS) fixed bearing knee (Zimmer Inc., Warsaw, Indiana, USA). All components are CE marked for the appropriate indications for use in this study.

#### **10. Outcome measures**

#### **Primary Outcome Measure:**

• Percentage of patients with a bi-phasic (normal) moment curve during gait (level walking) at one year – see section 8 for definition of bi-phasic gait.

# Secondary Outcome Measures:

- Percentage of patients with a bi-phasic (normal) moment curve during gait (level walking) at two years
- Biomechanical performance–Gait during stair climb/descent and lunge, functional activity assessment (using electrogoniometers).
- Activity Overall daily activity levels, maximum sport/physical activity, functional activity test times (stair climb, timed up and go)
- Impairment Range of motion, proprioception, quadriceps strength (short term outcome) and progression of OA in contralateral knee (long term outcome).
- Clinical Outcomes Clinical knee scores (Oxford Knee Score and New American Knee Society Score, Forgotten Joint Score), pain, analgesic use, complications, implant fixation and satisfaction.
- Safety profile (Determined by revision rate, adverse events, robotic system errors and accuracy of implantation)
- Accuracy of surgical implantation (determined by post-op CT analysis)

# 11. Assessment and follow up

Patients will be assessed pre-operatively and then post-operatively in clinic at 3 months, 1 year, 2 years, 5 years and 10 years. Patients will also complete personal diaries over the first 6 weeks post-op, these will record pain (VAS), function and analgesic use daily for the first 2 weeks and

weekly thereafter. Table 1 defines the follow up regime for both study groups. At 3 months post-operatively all patients will have a full leg CT scan of the operated limb. At 1 year post-operatively, in addition to clinical assessments, all patients will undergo full gait analysis, functional knee assessment, knee proprioception testing and participate in 5 day activity monitoring.

Time point Assessment	Pre-Op	0-6 weeks	3 Month	1 Year	2 year	5 Year	10 Year
Clinical					J U		
Oxford Knee Score	х		Х	Х	х	Х	Х
New American Knee Society Score (2012 version)	X		х	Х	Х	Х	Х
Forgotten Joint Score			Х	Х	Х	Х	Х
EQ-5D	Х			Х	Х	Х	Х
Pain (VAS)	Х		Х	Х	Х	Х	Х
X-ray (AP and lateral knee)	Х		Х	Х	Х	Х	Х
X-ray (long leg standing)	Х			Х			
CT scan (Knee)	Х		Х				
Satisfaction	Х		Х	Х	Х	Х	Х
Patient diary – Pain, function, Analgesic use		Х	х	Х			
Complications	Х		Х	Х	Х	Х	Х
Assessment of contralateral knee	Х			Х	Х	Х	Х
Function and Activity							
Gait Analysis	Х			Х	Х		
Functional knee assessment	Х			Х	Х		
UCLA Activity Score	Х		Х	Х	Х	Х	Х
Active Pal Activity monitoring	Х			Х	Х		
Stair climb test	Х		Х	Х	Х		
Timed Up and Go Test	Х		Х	Х	Х		
Impairment							
Proprioception	Х			Х	Х		
Range of motion	Х		Х	Х	Х	Х	Х
Quadriceps strength testing	Х			Х	Х		
Stiffness (VAS)	Х		Х	Х	Х		
Patient Questionnaire					х	or X	*

#### Table 1:

\*Participants will be invited to complete a questionnaire at 2 or 5 years (if completed at 2 years, not necessary to complete again, but if not done at 2 years, this can be completed at 5 years) to capture participant's impressions on the surgery they thought they had received, and this will allow us to investigate the effect of patient bias on the results.

In addition to these research clinic visits, we will compile a newsletter which will be sent out to participants when all recruited participants have reached 4 and 9 years post-op. Due to the length of time between research visits, this will serve to maintain participant engagement

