# 15. Sample size

The primary outcome measure is proportion of patients in each arm with a bi-phasic (normal) gait. 23% of TKA patients have a bi-phasic gait after surgery compared to 70% of UKA patients. Bi-UCKA surgery is unlikely to achieve quite the same level as UKA, nevertheless it is anticipated that a substantial proportion of this effect should be achievable. We therefore believe that 60% of Bi-UCKA patients might have a normal bi-phasic gait after surgery. To detect a difference of this size with a power of 90% at a 5% level of significance using a chi-squared test we would need to study 36 patients per group (calculated using 'sampsi' in Stata 11.2 without continuity correction). We will allow an additional 10% for loss to follow up at 1 year and will therefore study 40 patients per group (80 in total) recruited over 41 months. All patients will be recruited at Glasgow Royal Infirmary and will be operated on by one of three surgeons and randomisation will be stratified by surgeon. It is expected that each surgeon will conduct roughly similar numbers of operations, in both randomised groups. We will adjust for any clustering generated within surgeon by fitting surgeon as a random effect, and would expect to recover and possibly have a net increase in power by adjusting for pre-specified baseline covariates that would be strongly associated with 1 year outcome.

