# 21. Project timetable: Stages, Go/No-Go Decision Points and Milestones

We have assumed that contracts will be agreed and signed between NHS GGC and DoH by June 2013. We will allow 6 months prior to study initiation in order to obtain appropriate approvals, recruit staff and set up the study. Recruitment will begin in Dec 2013 and will last for 41 months.

Patient follow-up will last 10 years from the time of surgery, meaning that the final patient assessment will be at the end of July 2028. It is vital that patients are followed up for a minimum of 10 years in order to establish long term performance of this novel surgical method. Although we will follow up patients for a 10 year period, the primary knee kinematic data and early surgical outcome data will be collected 1 year after surgery has been completed on each patient. 1 year data collection will be completed by the end of July 2019. We will therefore analyse our 1 year data during August - September 2019 and will aim to have the first sets of publications arising from the study submitted by winter 2019. Subsequent publications will be produced end of 2020 (2 year data), 2023 (5 year data) and 2028 (10 year data).

Critical stages (with Go/No-Go decision points) and Milestones are given in table 2 below.Table 3 contains a gantt chart with key study timelines. A study recovery plan was submitted to the funder to permit the extension of recruitment from a period of 24 months to 41 months. This was granted and the resulting study timeline updates are reflected in Table 3.

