# Table 2: Study stages with Go / No-Go decisions and Milestones

# Table 3: Study Timeline (Gantt Chart)

				Years0 – 4 (6 month intervals)				Years 5-15 (Yearly intervals)														
Stage/Task	Start	End	Duration	0 - 6	6- 1 2	12 - 18	18 - 24	24 - 30	30- 36	36- 42	42 - 48	Хс 5	e Xr	¥ r 7	8 8	лу е	¥с 10	Уг. 11	Уг 12	ұг 13	پر 14	لار 15
Funding approved/contracts signed – Trial start	Sept 2014	-	-																			
Approvals: Ethics, R&D, MHRA	Sept 2014	Νον 2014	2 months																			
Staff recruitment	Sept 2014	Νον 2014	2 months																			
Trial set up	Sept 2014	Νον 2014	2 months																			
Patient recruitment	Dec 2014	Mar 2018	41 months																			
Surgery	Jan 2015	Apr 2018	41 months																			
Patient Follov+up (up to 10 years)	Apr 2015	July 2028	13 years																			
Data Analysis	After 1 comple		10 year follow up																			
Data Reporting	After 1 comple		10 year follow up																			
Publication drafting	After 1 comple		10 year follow up																			
Publication/dissemination	After 1 comple		10 year follow up																			
Trial Close	-	Dec 2028																				

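### Newsletters are timed by the last patient to reach 4 and 9 years, so the second reaches many patients after their final visit and the first misses their 2-to-5-year gap

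*Protocol*

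**What the plan says.** The notes under Table 1 in Section 11 provide for a newsletter to be mailed "when all recruited participants have reached 4 and 9 years post-op". The reason given is: "Due to the length of time between research visits, this will serve to maintain participant engagement".

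Visits follow a different clock. Section 11 has patients seen "post-operatively in clinic at 3 months, 1 year, 2 years, 5 years and 10 years", and Section 21 states: "Patient follow-up will last 10 years from the time of surgery". The 5- and 10-year visits are therefore anniversaries of each patient's own operation.

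Operations were spread over more than three years. Section 15 plans for "40 patients per group (80 in total) recruited over 41 months", and the surgery row of Table 3 reads "Surgery Jan 2015 Apr 2018 41 months".

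Section 21 stresses the long-term phase: "It is vital that patients are followed up for a minimum of 10 years in order to establish long term performance".

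**The concern.** The word *all* makes the last operated patient the clock for both mailings. A patient treated early in the surgery window can be more than three years ahead of that clock, while the newsletter leads the next visit by only one year (4 before 5, 9 before 10). For such a patient the visit comes first and the newsletter follows.

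What is at stake is retention in the long follow-up phase. The revision-rate question (Section 6), progression of osteoarthritis in the other knee (Section 10) and the 5- and 10-year scores in Table 1 all depend on patients returning, and only 80 are planned. The newsletter is the only contact between visits that Section 11 describes for keeping participants engaged.

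**Working it through.** **Inputs**
- Trigger: all participants at 4 years, then all at 9 years after surgery (Section 11).
- Visits: 5 and 10 years after the patient's own surgery (Sections 11 and 21).
- Surgery window: Jan 2015 to Apr 2018, stated as 41 months (Table 3).
- Number of patients: 80 (Section 15).
- Accrual over calendar time: not stated. Even accrual is assumed, with linearly rising and linearly falling rates as the range.
- Visits are taken to occur on the anniversary of surgery.

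**Window length.** Jan 2015 to Apr 2018 is 3 × 12 + 3 = 39 months elapsed, or 40 counted inclusively, against the stated 41. Section 21 puts the last assessment at the end of July 2028. If that means a last operation in July 2018, the window is 42 months elapsed or 43 inclusive. I therefore use T = 39 to 43 months, with 40 as the central value. Section 21 starts recruitment a year earlier than Table 3 (Dec 2013 against Dec 2014). Both give 41 months, and only the length of the window enters the share.

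**Mailing dates.** Apr 2018 + 4 years = Apr 2022. Apr 2018 + 9 years = Apr 2027.

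**Who is mailed after the visit.** The 5-year visit precedes the first mailing if surgery + 5 years falls before last surgery + 4 years, that is, if surgery was more than 12 months before the last one. The 10-year visit and the second mailing give the same condition, because 10 − 9 = 5 − 4. On Table 3's dates these are the patients operated on before about Apr 2017.

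**Share affected.** With c = (T − 12)/T, the share is c under even accrual, c² if the rate rises linearly from zero, and 1 − (1 − c)² if it falls linearly to zero.

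| T (months) | Even accrual | Of 80 | Rising | Falling |
|---|---|---|---|---|
| 39 | 27/39 = 69.2% | 55.4 | 47.9% | 90.5% |
| 40 | 28/40 = 70.0% | 56.0 | 49.0% | 91.0% |
| 41 | 29/41 = 70.7% | 56.6 | 50.0% | 91.4% |
| 43 | 31/43 = 72.1% | 57.7 | 52.0% | 92.2% |

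The accrual pattern matters far more than the exact window. The July 2028 date could instead reflect a three-month allowance after each anniversary. If every visit used that allowance in full, the even-accrual share at T = 40 would be (40 − 15)/40 = 62.5%, and the rising-accrual share 0.625² = 39%.

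**Where the earliest patients stand (T = 40).** At the first mailing they are 4 + 40/12 = 7.3 years post-op, and at the second 9 + 40/12 = 12.3 years. So the first newsletter reaches the affected patients between 5 and 7.3 years, at least 10 − 7.3 = 2.7 years before their 10-year visit. The second reaches them up to 2.3 years after it.

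**The case against.** The strongest reply is that the stated purpose is engagement between visits, and on that test the first newsletter still does something for everyone. Patients past their 5-year visit receive it inside the 5-to-10-year gap, the longest in the schedule. The rest receive it at 4 to 5 years. That stands. A reader might infer that both newsletters are wasted on early patients, but this is true only of the second. The first fails only to cover their 2-to-5-year gap.

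Three other stronger readings also lack support.
- *That the newsletters exist to secure the 5- and 10-year visits in particular.* The timing at 4 and 9 years suggests it, but the protocol speaks only of engagement over long intervals.
- *That extending recruitment from 24 to 41 months broke a rule that had worked.* The amendment history lists the newsletter and the extension under the same amendment. At 24 months the even-accrual share would already have been 12/24 = 50%.
- *That missing the earliest patients biases the comparison.* Allocation is randomised and stratified by surgeon, so early patients should fall in both arms.

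It is also fair to say that the sentence may be loose drafting for each participant's own 4- and 9-year date. The text does not say so, and the same edit settles it. Finally, no effect of a newsletter on attendance is given, and the only observed loss to follow-up reported is 8% (rationale for the sample size amendment). The shares above count mailing dates, not lost data.

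**Conclusion.** The point holds, at minor severity. As written, the trigger sends the second newsletter after the final visit to every patient operated on more than 12 months before the last one, and sends those patients the first newsletter after the 2-to-5-year gap has closed. About 70% are affected under even accrual, and roughly 50% to 91% under linearly rising or falling accrual. These figures rest on the literal reading of the trigger, on a window of about 40 months and on visits held at the anniversary; later visits would lower them.

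Only long-term engagement is touched. The 1-year primary outcome and the 2-year outcomes are not affected, and the consequence for 5- and 10-year attendance cannot be quantified from the protocol.

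**What to change.** Change the sentence in Section 11 so that each newsletter is timed from the participant's own operation, at 4 and 9 years after it. If individual mailing is impractical, group participants by 12-month periods of surgery and mail each group when its last-operated member reaches 4 (then 9) years. Every patient is then reached before the 5- and 10-year visits, and the share mailed late falls to zero.

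The cost is one sentence and a few batches instead of one mailing: 40/12 = 3.3, so four batches per newsletter. The content need not change. Version 4.2 is dated March 2021, so on the protocol's dates neither mailing was yet due when it was issued.

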#### Gait analysis, functional knee assessment and dynamic proprioception:

Biomechanical Gait and Stair analysis will be carried out using our 12 camera VICON Nexus system in the Bioengineering Unit (University of Strathclyde). Gait will be recorded during flat walking, stair ascent/decent and lunge movements allowing comparison between the two

surgical treatment options. We will also make comparisons with existing data from age matched controls. We have collected aged match data from 84 control subjects and therefore do not need to recruit any further control subjects. The following Kinetic parameters will be defined by this analysis: number of subjects with bi-phasic sagittal moment pattern at the treated knee, maximum flexion and extension moments for both limbs (Nm), and maximum adduction and abduction moments (Nm).

The primary outcome measure for the study will be proportion of patients in each group with a bi-phasic sagittal knee moment pattern during gait. We will define a Biphasic gait as one in which a significant knee flexion and extension moment are generated during stance phase of gait. Our system reports Flexion moments with a positive value and Extension moments with a negative value. In order for a patient to be classified as having "Bi-phasic Gait", the patient must produce a moment pattern with both flexion (positive) and extension (negative) values – this can be assessed by looking at the maximum and minimum moment values and verifying that the maximum value has a positive value and minimum a negative value. Patterns that have either all positive or all negative max and min values will be defined as non-Bi-Phasic. Hence the decision as to whether a bi-phasic gait in stance exists will be produce without subjective inference from the researchers carrying out the test.

Functional knee kinematic data will be derived from analysis of patients undertaking 13 tasks that are common in everyday living: Level walking, ascent of a 5 degree slope, descent of a 5 degree slope, ascent of a 20 step flight of stairs, descent of a 20 step flight of stairs, descent from standing into a low chair, ascent from a low chair to standing, descent from standing into a standard chair, ascent from a standard chair to standing, getting down to a squatting position, getting up from a squatting position a deep lunge with the left leg and a deep lunge with the right leg. Electrogoniometers will be used to record knee joint angles continuously during these activities.

In order to assess dynamic proprioception we will record patients' ability to maintain a static position during one legged stance; measuring sway area during a 30 second period. This will be carried out for both the operated and non-operated limb, pre and post-operatively.

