# 7. Research design

The study will be a prospective randomised double blinded controlled study comparing two surgical techniques. Patients randomised to Group 1 of the study (controls) will receive a standard TKA. Patients randomised to group 2 will receive Bi-UKA surgery carried out with the aid of Robotic Assistive Technology.

The study will be blinded, meaning that researchers undertaking post-operative patient assessments will not be informed which intervention patients have been randomised to receive. Surgeons involved in the study will be aware of which arm of the study patients have been randomised to. However, all post-operative data relating to the study will be collected by independent research nurses and no post-operative data will be collected by the operating surgeons. Patients will not be directly informed which arm of the study they have been randomised to.

Randomisation will be carried out after informed consent has been obtained and prior to the day of surgery. This duty will be carried out by research nurses and not by the investigators. A webbased interface will be used to access a dedicated randomisation programme created by the NIHR registered Clinical Trials Unit at the University of Aberdeen's Centre for Healthcare Randomised Trials (CHaRT) which is supporting the trial. Randomisation for the study will be stratified by surgeon.

Pre-operative and post-operative data collection will be carried out by research nurses at the time points specified in this protocol. Data will be collected on paper Case Report Forms (CRF) and this will be transcribed into a secure database. We have successfully used similar methodology for several other randomised controlled trials.

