# 16. Statistical analysis

All statistical analyses will be governed by a comprehensive Statistical Analysis Plan, which will be agreed by the research group and approved by the independent Data Monitoring Committee. The primary outcome (at 1 year) will be analysed according to the intention to treat principle, and will use a mixed effects logistic regression model, with surgeon fitted as a random effect. We will also consider a per protocol analysis, including those who received the surgery as intended. We would adjust this primary analysis for baseline gait i.e. the primary outcome measured at baseline. At present there are no subgroup analyses proposed for the primary outcome.

Analysis of secondary outcomes will be similar to that for the primary outcome, except using generalised linear models appropriate to the distribution of the specific outcome (e.g. linear or logistic). At present there are no count data (e.g. Poisson or negative binomial regression) or time to event outcomes (e.g. Cox proportional hazards regression) being considered. For the secondary outcomes that have serial measures post randomisation (e.g. 3m, 1 y, 2y, 5y, 10y) we will use repeated measures models to explore any possible time development of a treatment effect we identify.

As indicated above, we will explore the robustness of any findings we report to patterns of missing data, most prominently using multiple imputation models exploring missing data mechanisms assumed to be generated under a 'missing at random' assumption. There will be no formal adjustment for multiple comparisons given the explanatory rather than confirmatory nature of this study.

The independent Data Monitoring Committee will not conduct any formal interim analyses of the efficacy outcomes – their role will be primarily concerning safety.

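### Peak knee moments are stated in absolute Nm, with no limit on BMI and controls described only as age matched; stating them in Nm/kg would be a minor, cheap improvement

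*Protocol*

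**What the plan says.** The gait analysis part of Protocol section 11 names the kinetic parameters to be derived. Besides the number of patients with a bi-phasic pattern, they are "maximum flexion and extension moments for both limbs (Nm), and maximum adduction and abduction moments (Nm". The same part says "We will also make comparisons with existing data from age matched controls" and "We have collected aged match data from 84 control subjects". It gives no matching factor other than age and no body size for the controls.

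Section 8 lists "Patients of any BMI" among the inclusion criteria. Section 7 states: "Randomisation for the study will be stratified by surgeon". No other stratification factor is given.

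The primary outcome uses the same moment curve but only its signs. It is assessed by "verifying that the maximum value has a positive value and minimum a negative value".

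Section 16 says of the primary model: "We would adjust this primary analysis for baseline gait i.e. the primary outcome measured at baseline". It then says: "Analysis of secondary outcomes will be similar to that for the primary outcome". Section 15 mentions adjustment for pre-specified baseline covariates, but section 16 names only baseline gait. The protocol nowhere divides moments by body mass or height, and it names no body-size covariate.

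**The concern.** A joint moment is a force times a lever arm, so it rises with body mass and limb length. Two people who walk identically but differ in mass have different peaks in Nm. Two comparisons are touched, in different ways.

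- **Patients against the 84 controls.** This comparison is not randomised. If the groups differ in body mass, part of any difference in mean Nm reflects mass rather than gait. Age matching does not prevent that.
- **Bi-UCKA against TKA.** Randomisation protects against systematic bias. Body size can still add variance and chance imbalance, because BMI is unrestricted and not a stratification factor.

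The protocol itself states the unit, so this is not a detail it merely leaves to the analysis plan. The stake is limited to how these descriptive and mechanistic parameters are read.

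**Working it through.** **1. The plan's own figure.** Section 15 gives 23% against 60%, 90% power, 5% significance, and a chi-squared test without continuity correction. Taken as two-sided:

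n = [1.960·√(2·0.415·0.585) + 1.2816·√(0.23·0.77 + 0.60·0.40)]² / 0.37² = (1.366 + 0.828)² / 0.1369 ≈ 35.1, so 36 per arm (power 90.7%). Then 36/0.90 = 40 per arm. The stated 36 and 40 reproduce.

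**2. Primary endpoint.** Dividing the maximum and minimum by a positive body mass cannot change their signs. The bi-phasic classification, 36 and 40 are the same in Nm and in Nm/kg.

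**3. Comparison with controls.** Assume that the moment is proportional to mass and that mass is independent of the normalised moment. With equal normalised moments, the ratio of mean raw moments equals the ratio of mean masses.

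| Patients heavier by (assumed) | Spurious difference in mean Nm | In SD units (moment CV 0.5 to 0.3, mass CV 0.20) |
|---|---|---|
| 0% | 0% | 0 |
| 10% | 10% | 0.18 to 0.27 |
| 20% | 20% | 0.37 to 0.55 |

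For a peak with a larger CV, the same percentage is a smaller fraction of an SD.

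**4. Between arms, general formula.** With CVk for the normalised moment and CVm for body mass,

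variance inflation = [(1 + CVk²)(1 + CVm²) − 1] / CVk² = 1 + CVm²(1 + 1/CVk²).

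The protocol gives neither CV. CVm is taken as 0.15 to 0.25.

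**5. Sagittal peaks that straddle zero.** Section 15 expects 23% (TKA) and 60% (Bi-UCKA) to be bi-phasic. By the sign rule, 77% and 40% then have a maximum that is not positive or a minimum that is not negative. These failures fall evenly on the two peaks, all on one, or in between. For a normal variable with wrong-sign probability p, CVk = 1/|z(p)|.

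| Wrong-sign rate p | Source | CVk | Inflation at CVm 0.15 / 0.20 / 0.25 |
|---|---|---|---|
| 20% | Bi-UCKA, even split | 1.19 | 1.04 / 1.07 / 1.11 |
| 38.5% | TKA, even split | 3.4 | 1.02 / 1.04 / 1.07 |
| 40% | Bi-UCKA, one peak | 3.9 | 1.02 / 1.04 / 1.07 |
| 77% | TKA, one peak | 1.35 | 1.03 / 1.06 / 1.10 |

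The inflation is about 2% to 11%. Thirty-six per arm is worth about 36/1.11 ≈ 32 to 36/1.02 ≈ 35.

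**6. Peaks with a low CV.** A sagittal peak that rarely changes sign, or the frontal-plane moments, may have a CV near 0.4 (assumed). At CVm 0.20 without adjustment, the inflation is 1 + 0.04·(1 + 1/0.16) = 1.29, and 36/1.29 ≈ 28 per arm.

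Section 16 implies adjustment for the pre-operative value. The pre-operative raw moment carries much of the same body mass. A simulation (log-normal mass and moment, moment CV 0.4) gave these inflations after that adjustment:

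| Baseline correlation of normalised moment | CVm 0.15 | CVm 0.20 | CVm 0.25 |
|---|---|---|---|
| 0 | 1.14 | 1.24 | 1.35 |
| 0.3 | 1.09 | 1.16 | 1.22 |
| 0.5 | 1.07 | 1.11 | 1.16 |

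The unadjusted values are about 1.16, 1.29 and 1.45. Adjustment reduces the loss without removing it: 7% to 35% remains.

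**The case against.** **Not named outcomes.** Section 10 does not list the peak level-walking moments among the primary or secondary outcomes, and no test or sample size is attached to them. The bracketed Nm may be only the measurement unit, with the scale of analysis left to the analysis plan that section 16 says governs all analyses. This stands as a reason to rate the point low. It does not remove the point, because the only scale the protocol gives is absolute.

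**Absolute load can be relevant.** Section 4 links gait and moments to mechanical overload, component migration and loosening. In addition, a ratio between a patient's two limbs cancels body size. Both stand, and they justify keeping raw Nm as a supplement.

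**The control comparison may not use Nm peaks.** The protocol says only that comparisons will be made. Bi-phasic proportions and joint angles do not scale with mass. This stands too: the bias is conditional.

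**Stronger readings.** A reader might assume a CV of 0.25 to 0.45 for every peak and infer inflation of 13% to 106%. The low bi-phasic rates in section 15 do not support that for every peak, since at least one sagittal peak must then straddle zero, with a CV above 1 under normality. A reader might also infer that the arm comparison is biased. Randomisation rules out systematic bias there.

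**Conclusion.** The point holds as a minor improvement. The protocol states peak moments in absolute Nm, enrols without a BMI limit, and plans a non-randomised comparison with controls described only as age matched.

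- **Against controls:** a possible bias in mean raw moments equal to the proportional difference in mean mass. Its size and direction are unknown, because the protocol gives neither group's body mass. A reader might conclude that the comparison is biased, but the protocol shows only that it is unprotected. With equal masses the bias is zero.
- **Between arms:** added noise of about 2% to 11% for peaks that straddle zero, and perhaps 7% to 35% after baseline adjustment for peaks with a CV of about 0.4.
- **Primary endpoint and sample size:** unaffected.

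These sizes rest on moments proportional to mass, mass independent of normalised gait, normality for the peaks that straddle zero, and CVs that the protocol does not give.

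**What to change.** In the gait analysis part of section 11, define the peak flexion, extension, adduction and abduction moments as Nm/kg, using body mass measured at the same gait session. Apply this to patients at every gait visit and to the 84 controls. Use the normalised values in both the arm comparison and the control comparison, and keep raw Nm as a supplementary description of absolute load.

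The cost is one reworded sentence and one extra derived variable. It requires that body mass was recorded in both data sets, which is assumed because the protocol does not say so. If it was not recorded for the controls, the comparison of peak moments with them should carry that caveat. The bi-phasic rule and the sample size need no change.
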